In 2013, Ospemifene was approved by the Food and Drug Administration for the treatment of moderate to severe dyspareunia that is due to menopause [10]. Ospemifene is a non-estrogen selective estrogen receptor modulator (SERM). SERMs are estrogen receptor (ER) agonist/antagonists that typically induce the desirable effects of estrogen while avoiding estrogen-related adverse effects. Unlike other drugs in this class, Ospemifene has been shown to have significant estrogenic agonist effects on the vagina and bone, but antagonist effects on breast tissue [6]. Furthermore, it significantly improves overall sexual function [12]. Despite this promising medical profile, it remains a second or third line of therapy to treat VVA. More research is needed to determine if ospemifene is an acceptable, and possibly a favorable, alternative to vaginal estrogen for the treatment of vulvovaginal atrophy, especially if there is any concern for sexual function. In this research study, we aspire to determine the efficacy of ospemifene compared to a vaginal estrogen. The primary aim of this research is to compare female sexual function as measured by a validated instrument in women randomized to receive ospemifene and vaginal estrogen. Secondary aims include comparing markers of vaginal health and safety in both treatment groups.

Hypothesis

Ospemifene is a nonhormonal alternative that has proven to significantly improve sexual health and vulvovaginal atrophy, yet vaginal estrogen is still considered the first-line therapy. Our null hypothesis is that ospemifene has a similar efficacy as vaginal conjugated estrogens for improving sexual function in postmenopausal women who have vulvovaginal atrophy.

Specific Aims

Specific Aim 1: *To compare the efficacy of ospemifene and vaginal conjugated estrogens on female sexual function.* Ospemifene is the only non-estrogen that is FDA-approved to treat dyspareunia in postmenopausal women. Further, studies report a significant improvement in sexual health in patients that are treated with ospemifene [12]. However, vaginal estrogen therapy (with conjugated equine estrogen or estradiol) remains the most commonly prescribed treatment for dyspareunia. To our knowledge, a direct comparison of ospemifene and local vaginal estrogen therapy on postmenopausal female sexual function has not been performed. We hypothesize that ospemifene provides a greater improvement in sexual function in postmenopausal women with dyspareunia and VVA.

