There are a few effective treatment options for VVA. The most commonly used treatment is vaginal estrogen. This is prescribed in various forms, including a vaginal cream (Estrace, Premarin, compounded), a vaginal tablet (Vagifem), and a vaginal ring (Estring). Aside from the ring, the medication dosing typically involves nightly dosing for two weeks, followed by dosing twice per week. Estrogen functions by improving the percentage of vaginal superficial cells, while decreasing the pH, and improving symptom scores in participants [14,5]. Studies have also shown that the serum estradiol levels remained below 20mcg/mL, which is the typical maximum optimum estradiol level in PMP women [15]. Other related estrogens, particularly estrone and estrone sulfate, also remained within postmenopausal levels [14]. With these findings, many clinicians feel comfortable recommending vaginal estrogen to patients who suffer from symptomatic vaginal atrophy. However, estrogen's causal relationship with breast cancer and endometrial cancer causes many women to avoid using vaginal estrogen [16]. Hence, treatment options that do not involve the introduction of estrogen into the bloodstream are likely to be well sought after.

Ospemifene

Ospemifene is a selective estrogen receptor modulator (SERM), and it is the only SERM approved in the United States to treat moderate to severe dyspareunia associated with VVA [6,17].

It is an oral medication that is taken as a 60mg tablet once daily. Food intake increases its absorption by 2 to 3-fold, and this is not impacted by the fat or calorie content of the food. It is metabolized primarily in the liver, and is excreted in feces [4]. SERMs are estrogen receptor (ER) agonist/antagonists that typically induce the desirable effects of estrogen while avoiding estrogen-related adverse effects. Ospemifene is unique within this class because in addition to its protective activity in bone and breast tissue, it has a significant beneficial influence in the vagina without a carcinogenic effect on the endometrium. Initially, the drug was developed because of its bone-sparing reduction of bone resorption in OVX rats. However, its performance in other hormone-sensitive tissue led to further investigation [17].

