In its clinical development, ospemifene was singled out because unlike tamoxifen and raloxifene, ospemifene significantly improves vaginal maturation. As a non-estrogen substance, its mechanism involves activation of estrogen receptors in the vagina, which leads to an increased thickness, mucification, and vacuolization of vaginal epithelium [18]. Several RCTs have shown an improvement in VVA with the use of ospemifene compared to placebo [6]. Importantly, the serum estradiol levels have been documented as unchanged in patients that use the medication for 12 weeks [19].

Equally important is the activity of ospemifene in mammary tissue. In ER+ human breast cancer cells, ospemifene has either had no impact, or has had a dose-dependent growth inhibitory effect [20,21]. This implies its dependence on ER-alpha expression in this tissue. Two studies examined ospemifene's ability to prevent dimethylbenzanthracene (DMBA)-induced breast cancer in mice. For up to 52 weeks of drug exposure, ospemifene prevented breast tumor formation similarly to tamoxifen [22]. Moreover, in normal human breast tissue, ospemifene also has similar antiestrogenic inhibitory effects as tamoxifen [23].

An additional pilot study involving ospemifene administration to rhesus macaques suggest that it has a lower carcinogenic potential than tamoxifen, which is another SERM that is used in breast cancer treatment and prevention. In this study, there was no evidence of DNA adduct production in the liver or the endometrium from daily ospemifene, while tamoxifen, the positive control, showed production of several DNA adducts in each organ [24]. Furthermore, clinical trials mirrored animal studies in that there was an increase in uterine weight and proliferative tissue, but there has never been any evidence of endometrial hyperplasia or bleeding with use of ospemifene [25,26]. These findings have been strengthened by six RCTs, where no cases of endometrial hyperplasia or cancer has been identified [6].

Sexual Health

As may be expected, VVA is four times more likely in patients who suffer from sexual dysfunction [14]. Ospemifene is FDA-approved specifically for dyspareunia in postmenopausal women with VVA. Studies show that it also improves the overall sexual health for women [12]. While estrogen has been shown to improve dyspareunia and lubrication, its impact on overall sexual health is not well-identified [27].

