In essence, Ospemifene seems to be a possible wonder drug for menopausal women. While it's primary use is for VVA-associated dyspareunia, there is consistent evidence of protective activity in bone and breast tissue, while showing no evidence of carcinogenic potential in the endometrium, breast, or liver. Similar to vaginal estrogen, ospemifene has not been studied longer than 12 months to determine long term risks of the medication [6]. Appendix 1 shows a summary of adverse events in various safety studies for vaginal estrogen and ospemifene. Research is

promising that Ospemifene may prove to be a safer and more beneficial choice for all postmenopausal women, regardless of their history of breast or endometrial cancer.

Innovation

Several studies have published data regarding the unique behavior of ospemifene in postmenopausal women. Nonetheless, vaginal estrogen is still seen as the gold standard for the treatment of VVA, regardless of the woman's most bothersome symptom. To our knowledge, for the first time, this study will directly compare the efficacy of vaginal conjugated estrogens and ospemifene in improving sexual function in postmenopausal women who have vulvovaginal atrophy. By also directly comparing symptom improvement with VVA treatment, this study hopes to answer the question of whether or not clinicians should shift towards ospemifene as a first line treatment for sexual dysfunction in postmenopausal women with VVA.

Approach

Overview

This study will be a prospective, randomized study that will compare efficacy and safety of ospemifene and vaginal estrogen. Because of the route of administration for each drug, it is not possible to blind the participants or clinicians to the treatment. However, we will be collecting objective data that cannot be misinterpreted by those collecting and analyzing the data. We hope to effectively inform clinicians who treat postmenopausal women that suffer from VVA about the efficacy of ospemifene as it compares to vaginal conjugated estrogens cream. As a specialty with a high population of patients who complain of VVA, we are very familiar with this patient population, as well as the use of vaginal estrogen in their treatment. This puts this research team in an ideal position to properly execute the study and interpret the findings.

Patient Groups

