All research activities will be performed after obtaining Institutional Review Board Approval from Emory University. A consecutive sample of women will be recruited from the FPMRS and Menopause patients within The Emory clinics. Subjects are identified after their management plan has been established to include treatment of vulvar and/or vaginal atrophy. Patients will be approached by the principal and/or co-investigators. For women that agree to participate, written informed consent will be obtained. All women who agree to participate in this study must meet inclusion criteria listed in Table 1. Once the exclusion criteria have been applied (Table 2), the qualifying subjects will be enrolled in the study. Once enrolled, each subject will complete the Female Sexual Function Index (FSFI) questionnaire and a symptom severity Likert scale. Finally, they will receive instructions on medication compliance, as well as potential adverse events for the designated medication. If we assume 50% of women offered enrollment in this study will agree and be eligible to participate, we expect to reach our target enrollment in seven to eight months.

Table 1. Inclusion Criteria
Interested in resuming or continuing sexual activity

Table 1. Inclusion Criteria

Greater than 12 months since last menstrual cycle or prior bilateral oophorectomy
40yo or older
Dyspareunia as a vulvovaginal atrophy symptom
Normal mammogram within 12 months prior to entry into the study

Table 2. Exclusion Criteria

History or suspicion of breast carcinoma
History of hormone-dependent tumor
Genital bleeding of unknown cause
Ongoing vaginal infection
History of CVA, MI or heart disease, uncontrolled HTN over 160/100
Serious disease or chronic condition that may prevent completion of study, BMI over 40
Hypercoagulable state, or currently on anticoagulant therapy
Use of any exogenous sex hormone within three months from study entry, or during the study
Pelvic surgery within the last 12 months

Randomization and Allocation Concealment

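### Table 2 restricts recent use of sex hormones but, as worded, not of ospemifene, and prior treatment is not listed as recorded, so earlier benefit can enter the baseline unseen

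*Combined protocol and SAP*

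**What the plan says.** All references are to the combined protocol and SAP.

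- **Patient Groups, Table 2** excludes "Use of any exogenous sex hormone within three months from study entry", and the same line extends this to use while in the trial. No other line concerns hormonal or VVA therapy; the remaining treatment-related lines cover anticoagulants and pelvic surgery.
- **Hypothesis** states: "Ospemifene is a nonhormonal alternative that has proven to significantly improve sexual health and vulvovaginal atrophy". **Significance, Ospemifene** adds: "As a non-estrogen substance, its mechanism involves activation of estrogen receptors in the vagina". The drug is described as a SERM throughout, and no SERM restriction appears anywhere.
- **Patient Groups, Table 1** requires "Dyspareunia as a vulvovaginal atrophy symptom". It sets no condition on earlier treatment or response to it.
- **Patient Groups** gives the source of participants: "A consecutive sample of women will be recruited from the FPMRS and Menopause patients within The Emory clinics". **What is Vulvovaginal Atrophy?** says of the treatment options: "The most commonly used treatment is vaginal estrogen".
- **Patient Groups** lists the FSFI and a symptom severity scale as the enrolment questionnaires. Prior treatment is not named as a baseline item there, as a stratification factor under Randomization and Allocation Concealment, or as a covariate under Specific Aims.
- **Specific Aims** (after Sample Size Analysis) compares changes from baseline in the FSFI and in the most bothersome symptom (MBS).
- **Innovation** hopes to answer "whether or not clinicians should shift towards ospemifene as a first line treatment for sexual dysfunction in postmenopausal women with VVA".

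**The concern.** The two study drugs are treated differently at entry. A woman who used vaginal estrogen two months ago is excluded. A woman who took ospemifene last week is not, because the protocol's own vocabulary places that drug outside the term sex hormone. Both drugs act on vaginal tissue through estrogen receptors, so the reason for restricting recent use of one applies to the other. If earlier benefit is present at baseline, the change score no longer starts from an untreated state.

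The second part concerns information. A woman who stopped vaginal estrogen at least three months ago because it did not help, and who still has dyspareunia, is eligible and may be allocated to it again. That is a legitimate population to study. But her history is not among the listed data, so nobody could later say how far the result depends on such women. This matters because the stated hope is to guide first-line choice.

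**Working it through.** **Plan's own figure.** Inputs from Sample Size Analysis: 57% FSD, a 50% reduction (28.5%), alpha 0.05, power 0.80, 15% dropout. With the unpooled normal formula, two-sided:

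n = (1.960 + 0.842)² × (0.57×0.43 + 0.285×0.715) / 0.285² = 7.849 × 0.4489 / 0.0812 = 43.4, so 44 per arm; 44/0.85 = 51.8, so 52.

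The stated 52 per group reproduces, and nothing below changes it. I use 44 evaluable women per arm. The documents give no share of prior users or failures, so every share below is an assumption.

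**Carry-over at baseline.** Suppose a share g of women enter with b points of ospemifene benefit already in the baseline score, and their week-12 score depends only on the assigned drug. Each such woman's change is lower by b in either arm.

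- Mean change falls by g×b in both arms, so the expected between-arm difference does not move.
- The variance of change rises by g(1−g)b².

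With b = 4 FSFI points and SD of change 6 (both assumed):

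| g | Fall in mean change, each arm | SD of change |
|---|---|---|
| 10% | 0.4 | √(36 + 0.09×16) = 6.12 |
| 20% | 0.8 | √(36 + 0.16×16) = 6.21 |
| 30% | 1.2 | √(36 + 0.21×16) = 6.27 |

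In this simple case, change within each arm is understated and the comparison becomes slightly noisier. If the earlier benefit lasts to week 12 in the estrogen arm, or if prior users gain nothing more on ospemifene, the difference itself shifts against ospemifene. As an upper-end example on the FSD endpoint, let a share of the ospemifene arm stay at 57% instead of reaching 28.5%, with the estrogen arm at 57%. At shares of 10%, 20% and 30% the ospemifene rate is 31.4%, 34.2% and 37.1%. Power by the pooled test falls from 78% to 68%, 58% and 47%. (The 78% differs from the planned 80% because the pooled test is slightly more demanding than the unpooled formula.)

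**Prior failure of vaginal estrogen.** Suppose both drugs give 28.5% FSD in women without prior failure, everyone on ospemifene has 28.5%, and prior failures have 57% to 75% FSD when given estrogen again. The estrogen-arm rate is 0.285 + f×(q − 0.285), with f the share of failures and q their rate.

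| f | Estrogen-arm rate | Difference, points | Chance of declaring ospemifene better |
|---|---|---|---|
| 10% | 31–33% | 3–5 | 5–7% |
| 20% | 34–38% | 6–9 | 8–15% |
| 30% | 37–42% | 9–14 | 13–28% |

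The reference is 2.5% if the drugs are equal in everyone enrolled. If prior failures respond equally poorly to both drugs, the difference is 0 and the chance stays at 2.5%. On the FSFI scale (SD 6, standard error 6×√(2/44) = 1.28), a 1-point gap among failures at shares of 10% to 40% gives a difference of 0.1 to 0.4 points. The chance is then Φ(0.1/1.28 − 1.96) = 3.0% to Φ(0.4/1.28 − 1.96) = 5.0%. The answer depends mainly on how failures respond to each drug, on which the documents give no figure.

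**The case against.** The strongest reply is that randomisation balances treatment history in expectation, so the between-arm contrast is valid for the women enrolled. That stands. The aim under Specific Aim 1 covers postmenopausal women with dyspareunia and VVA and is not limited to untreated women. First-line use is a hope expressed under Innovation.

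It is also fair that recent ospemifene users are probably few. The Introduction calls the drug second or third line. Entrants must have current dyspareunia, and the investigators approach them after a treatment plan has been made. The Abstract and What is Vulvovaginal Atrophy? say many women avoid vaginal estrogen, which suggests a sizeable unexposed pool. These points limit the size of the problem, but none of them closes the gap in the wording.

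Three stronger readings are tempting, and the documents do not support them.

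- **That the rule favours ospemifene overall.** Prior estrogen failures could weigh against estrogen. Carry-over, or prior ospemifene failures (equally eligible), could weigh against ospemifene. The net direction is unknown.
- **That the false-positive rate is inflated.** If failures gain 4 points on ospemifene and 0 on estrogen, shares of 10% to 40% give a 5% to 24% chance of declaring ospemifene better. But under that assumption ospemifene truly is better in the enrolled women, so a rejection there is correct. The figures concern generalisation to first-line use, and they rest on an extreme response pattern that the documents do not state. Since ospemifene also acts through vaginal estrogen receptors, shared non-response is plausible.
- **That women with prior estrogen failure must be excluded.** Including them is a defensible design choice, provided their history is known.

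**Conclusion.** The point holds in a limited form. As worded, Table 2 restricts recent use of one study drug and not the other, and no other section corrects this. The consequence is possible carry-over into the baseline FSFI and MBS scores, which understates change within arms and blurs the comparison. The affected number is probably small, and neither size nor net direction can be derived from the documents.

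Separately, prior treatment and response are not listed as collected. The plan as written therefore cannot show whether the result also applies to women without prior failure of either drug, which is what a first-line conclusion needs. The conclusion rests on reading the exclusion with the protocol's own classification of ospemifene. Investigators might in practice treat a SERM as a hormone, but eligibility should not depend on that.

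**What to change.** 1. Amend the Table 2 line so that the restriction on recent use covers ospemifene and other SERMs as well as sex hormones. The investigators should set the interval. The part on use during the study should exempt the assigned drug.
2. Before allocation, record prior vaginal estrogen and ospemifene use and the reason for stopping each.
3. Report a sensitivity analysis of the FSFI and MBS comparisons in women without prior failure of either drug, and limit any first-line conclusion to what that analysis supports.

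**Cost.** One amended line, one screening question and perhaps a few lost candidates; the sample size does not change. The sensitivity analysis will be imprecise. With SD 6 assumed, the 95% half-width for the FSFI difference is 1.96×6×√(2/44) = 2.5 points with 44 per arm. It is 2.8 points with 35 per arm (about 20% set aside) and 3.0 with 30 per arm (about 30% set aside). It should be presented as supportive only.

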[name]

Ospemifene versus Conjugated Estrogens in the Treatment of Postmenopausal Sexual Dysfunction

[name]

Female Pelvic Medicine and Reconstructive Surgery, Fellow
Emory University

[name], PhD

Female Pelvic Medicine and Reconstructive Surgery, Division Director & Fellowship Director
Associate Professor
Emory University Hospital, Chief of Service

[name], MPH, NCMP

Department of Obstetrics & Gynecology, Associate Professor
Menopause Clinic, Director
Emory University

Abstract & Relevance

57% of postmenopausal women suffer from female sexual dysfunction (FSD). Vulvovaginal atrophy (VVA) is a condition that impacts up to 60% of the growing postmenopausal female population, and the most common symptom is dyspareunia. Women with FSD are 3.84 times as likely to also have VVA. Vaginal estrogen is the most common treatment for VVA, but it only marginally improves overall sexual function, and many women and clinicians avoid using it because of the risks of exogenous estrogen use during menopause. Ospemifene is a SERM that is FDA-approved for dyspareunia related to VVA, and has shown superb improvements in overall sexual health. This oral medication, taken daily, improves vaginal health, and has demonstrated protective activity in the breast and bone tissues. It also has not demonstrated any carcinogenic activity in the endometrium or liver. This study hopes to determine if ospemifene is superior to conjugated estrogens in improving sexual function and vaginal atrophy symptoms. 104 women will be randomized to receive 12 weeks of 60mg oral ospemifene, taken daily, or 12 weeks of 0.5mg vaginal conjugated estrogens, which is placed vaginally twice per week. The improvements in sexual health and VVA symptom severity will be compared in each group. This study will help determine if ospemifene is a better treatment medication than conjugated estrogens. The implications of this study may provide an attractive alternative to the many women who continue to suffer from sexual dysfunction and VVA because of concerns surrounding the use of exogenous hormones.

Introduction

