In May 2013, the Board of Directors of the International Society for the Study of Women's Sexual Health (ISSWSH) and the Board of Trustees of The North American Menopause Society (NAMS) endorsed the term genitourinary syndrome of menopause (GSM). This term encompasses the numerous changes that occur as a result of the decrease in estrogen and other sex steroids, including vaginal atrophy and sexual dysfunction [1]. In a cross-sectional study of US postmenopausal women, those with sexual dysfunction were 4 times more likely to have vulvovaginal atrophy [2]. With the rising elderly population, the impact of VVA and sexual dysfunction on quality of life and health care costs is a growing issue. In 2000, there were 26.25 million women over the age of 60 years old, and this number is expected to almost double by the year 2030 [3]. Currently VVA affects up to 60% of postmenopausal women, and its most common

Updated 11/27/17

Pg. 1

symptom is dyspareunia [4,5]. Further, if left untreated, it can increase rates of infection, and negatively impact a woman's sexual health and quality of life [6]. While only 25% of women with VVA seek medical advice, only 3% of women reveal problems with sexual health without being prompted [7,8].

There are several established methods of treatment for VVA. Vaginal estrogen is considered the treatment of choice. While several studies have shown that vaginal estrogen does not increase serum estrogen levels above postmenopausal values, there is still significant controversy surrounding the use of estrogen and the risk of breast cancer and uterine cancer [9,10]. This study is important because we hope to prove a non-estrogen medication to be an effective non-hormonal alternative therapy for vulvovaginal atrophy.

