Once a qualifying subject is identified, she will be randomized into a treatment group. The participant will be randomized to receive either a vaginal conjugated estrogens prescription or an ospemifene prescription. A computerized randomization program will be used to perform block randomization in random blocks of 4 and 10. Allocations envelopes containing the assignment will be used for the study. They will be sealed opaque envelopes with aluminum foil inside. They will also contain carbon-copy paper. The treatment number will be printed on the envelope. Once the participant has signed the informed consent form, her name will be printed on the envelope, which will transfer over to the carbon-copy paper, and the envelope will be opened.

Study Plan

The patient will be informed of her assigned medication, and she will receive a medication coupon to help offset the cost of the medication. Each medication is FDA-approved for long-term use of at least 52 weeks. For this study, a 12-week prescription for the medication will be sent electron-

[figure not shown]
ically to the pharmacy of her choice. Treatment with estrogen will consist of 0.5 gram of conjugated estrogens placed vaginally for 12 weeks. Treatment with ospemifene will consist of a 60mg tablet that will be taken at the same time daily for 12 weeks.

The patient will receive an intake packet that includes the following information:

1. Copy of signed informed consent form
2. Important contacts and instructions for emergency/adverse events
3. Allocation card
4. Medication's FDA packet insert
5. Instructions on dosing
6. 12-week date to repeat questionnaires

She will be called the following day to confirm her start date of the medication. They will return at 12 weeks and complete the same FSFI and Likert Scale questionnaires regarding sexual function and VVA symptoms. The questionnaires may also be completed over the phone with the investigator.

Alternatively, if time during clinic is limited, the patient can be consented and allocated to a medication in person, by a co-investigator. She will be called by a co-investigator on the same day to complete the enrollment and questionnaires. Below is a summary of the study plan.

Sample Size Analysis

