To our knowledge, there has been no prior study that reported the prevalence of female sexual dysfunction amongst women using vaginal conjugated estrogens, defined as having an FSFI score of 26.55 or less. With an FSD prevalence of 57%, we determine a 50% reduction in the prevalence to be clinically significant. Setting an alpha of 0.05, and a power of 0.80, and assuming a minimum of 15% dropout rate, the sample size is set to 52 in each group.

Specific Aims

Specific Aim 1: To compare the efficacy of each drug in improving sexual function.

- a. Experimental Design: In this study, participants will be asked to complete the 19-question female sexual function index (FSFI) questionnaire at the beginning of the study period and at 12 weeks. The results will be used to compare the effect of each medication on the various domains of sexual function.

The mean total score in each treatment group at baseline will be compared using Student's t-test. Additionally, the score of the components of desire, arousal, lubrication, orgasm, satisfaction and pain will be similarly compared. Later, the change in these scores between the two treatment groups at 12 weeks will be compared using a paired t-test analysis.

Anticipated Results and Interpretation: We expect to see similar results in this study, showing comparable improvements in vaginal lubrication and dyspareunia, while showing greater improvement for overall sexual health in the ospemifene group.

Potential Pitfalls, Alternative Approaches, and Future Directions: We do not anticipate any challenges with the administration and analysis of this questionnaire.

Specific Aim 2: To compare each drug's impact on VVA symptoms

- a. Experimental Design: Participants will complete a Likert scale of symptom severity at the beginning and at the end of the study. The symptoms listed will include dyspareunia, vaginal dryness, vaginal pain, and vaginal itching. The survey will ask them to rate the severity of each VVA symptom on a scale of 0 to 3, with 0 being none, 1 being mild, 2 being moderate, and 3 being severe. It will also ask them to choose their most bothersome symptom (MBS).

The mean score of the MBS in each treatment group at baseline will be compared using Student's t-test. Later, the change in score of the MBS between the two treatment groups at four weeks and again at 12 weeks will be compared using a paired t-test analysis.

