Appendix 1. TEAEs in Vaginal Conjugated Estrogens Cream and Ospemifene Trials				
	Ospemifene 60mg x 12 weeks [17]	Ospemifene 60mg x 52wks [7]	Vaginal CE 0.3mg x 12 weeks [30]	Vaginal CE 0.3mg x 52 weeks [30]
% w/ 1 or more TEAE	Not stated, 1892 exposed patients total, 1000 patient years of exposure	63.8%	71.4%	61.4%
Headache	2.4%		18.6%	14.4
Muscle spasm	3.2%			
Arthralgia				9.1
Vaginal discharge	3.8%			
Vaginal candidiasis or mycotic infection		4.3%		
Vaginitis				6.1%
Hot flashes	7.5%	7.2% (1.6% discontinuation rate)		
UTI	Similar to placebo	8.7% (8.2% for placebo)		
Vaginal bleeding			*1.4% of all groups	*1% of all groups
Proliferative endometrium				0.08%
Hyperplasia or cancer	0%	0%		0%
Cardiovascular events/VTE	0.3%	0%		
URI/Nasopharyngitis/Sinusitis		5% or more		
Pharyngolaryngeal pain		5% or more		
Hypercholesterolemia		5% or more		
Serious/Severe TEAEs <5%	0.13 per patient year (0.21 in placebo group)	5 participants with 7 TESAEs: breast prosthesis implantation, encephalitis herpes, non-cardiac chest pain, candida meningitis, gastritis, chronic obstructive pulmonary disease, and dehydration	5 participants from all groups, considered unrelated to study	6 participants from all groups, considered unrelated to study
TEAE: treatment-emergent adverse event; CE: conjugated estrogens; VTE: venous thromboembolism; *: study does not distinguish between placebo and the two treatment arms.

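### The abstract gives the comparator as 0.5mg of vaginal conjugated estrogens and the Study Plan gives 0.5 gram; no visible text says which is drug, which is cream, or how they relate

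*Combined protocol and SAP*

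**What the plan says.** Two sentences in the combined protocol and SAP define the estrogen arm by amount.

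- Abstract & Relevance: "12 weeks of 0.5mg vaginal conjugated estrogens, which is placed vaginally twice per week".
- Study Plan, in the paragraph on the prescription: "Treatment with estrogen will consist of 0.5 gram of conjugated estrogens placed vaginally for 12 weeks". The visible text of this section states no frequency for the estrogen.

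Other text bears on how to read them.

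- The Overview under Approach calls the product a cream: "the efficacy of ospemifene as it compares to vaginal conjugated estrogens cream". So does the title of Appendix 1: "TEAEs in Vaginal Conjugated Estrogens Cream and Ospemifene Trials". Neither place gives a strength for the cream.
- Randomization and Allocation Concealment uses the drug name as shorthand for the prescribed product: "either a vaginal conjugated estrogens prescription or an ospemifene prescription".
- Appendix 1 lists vaginal conjugated estrogens at 0.3mg. Those columns describe earlier trials and are not tied to this trial's dose.
- The Study Plan ends with "Below is a summary of the study plan". A figure in that section is not shown in the text available for review. The section also lists a dosing-instruction sheet and the package insert among the papers given to each woman, but does not reproduce them.

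The ospemifene dose is the same in both places: 60mg once a day for 12 weeks. Only the comparator is affected.

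**The concern.** Both sentences are current text, both are intact, and both attach their number to conjugated estrogens rather than to a cream or to an amount of active drug. On their face they give the same digits in units that differ by a factor of 1000.

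The trial is a head-to-head comparison, so the comparator dose defines half of what is being compared. A reader who has only the visible text cannot say how much estrogen ospemifene is set against. The same reader cannot relate the comparator to the 0.3mg columns of Appendix 1, the appendix that the Safety Monitoring section cites for known adverse events. The Study Plan sends each prescription to a pharmacy of the woman's choosing, and the visible text describes no central study pharmacy that would standardise the product.

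**Working it through.** The plan has no calculated figure to reproduce here. The check compares the amounts and converts the units.

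**Inputs**

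| Source | Amount | Frequency |
|---|---|---|
| Abstract & Relevance | 0.5 mg | twice per week, 12 weeks |
| Study Plan, visible text | 0.5 g | not stated, 12 weeks |
| Appendix 1 (earlier trials) | 0.3 mg | not stated in the column headings |
| Cream strength | not given in the visible text | – |

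**Step 1. Literal reading, both amounts as active drug.** 0.5 g × 1000 mg/g = 500 mg. Ratio: 500 mg / 0.5 mg = 1000.

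**Step 2. Cream-and-drug reading.** Suppose the Study Plan amount is cream and the abstract amount is the drug in it. They agree only if the strength is 0.5 mg / 0.5 g = 1.0 mg of drug per gram of cream. At any other strength they describe different doses. The visible text states no strength, so this cannot be tested from the documents.

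**Step 3. Which reading is more plausible.** Taken as active drug, the Study Plan amount would be 500 mg / 0.3 mg ≈ 1,667 times the amount in Appendix 1. With the product called a cream in two places and the drug name used as shorthand for it, a missing label (cream or drug) is plausible. It remains an inference, because no sentence states it.

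**Step 4. Reach into the statistics.** The Sample Size Analysis uses a 57% prevalence, a 50% reduction, alpha 0.05, power 0.80 and 15% dropout, and concludes "the sample size is set to 52 in each group". No dose enters. The questionnaires and planned tests do not depend on the dose statement either.

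**Step 5. Timing.** The document footer reads "Updated 11/27/17". The Timeline has recruitment ending on August 1, 2017. Twelve weeks (84 days) after that is October 24, 2017, so on the planned dates treatment would have finished before the update. Actual dates are not given.

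**The case against.** The strongest reply is that this is a labelling slip that no prescriber would act on. The Study Plan is the operative section and gives one amount; the other is in a summary. The drugs are described as FDA-approved, and each woman receives the package insert and dosing instructions. The product is a cream, so half a gram is naturally read as cream. The figure not shown sits within the Study Plan and could carry the strength. If it gave 1.0 mg per gram, the two sentences would agree in substance. On the planned dates, all treatment was over before the document was last updated.

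Most of this stands. It limits the point to how the arm is described and takes away urgency. Because the figure is missing from the review copy, its silence cannot be held against the plan. The reply does not remove the inconsistency: the two sentences still differ in unit, neither says what its number measures, and the reader must supply a strength that the visible text lacks.

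A reader might infer that women were prescribed a thousandfold wrong dose. The documents do not support that: they show no prescription, and the cream reading is plausible. A reader might also infer a conflict on frequency. There is none, since the abstract states a frequency and the visible Study Plan text is silent.

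**Conclusion.** The point holds as an inconsistency in the definition of the comparator. Read literally, the two amounts differ 1000-fold. Read as cream and drug, they agree at exactly one strength, 1.0 mg per gram, and whether that strength applies is undetermined from the visible text. The conclusion rests on the visible wording alone; the figure, the instruction sheet or the insert may supply the link.

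It would go too far to call this a demonstrated safety problem or a threat to the trial's validity. No dosing error is shown, and the endpoints, analysis and sample size do not change. The correction should be made, because a published comparison needs an unambiguous comparator, but nothing here shows that it must hold up the trial.

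**What to change.** The investigators must reconcile the abstract and the Study Plan into one statement of the comparator that gives the amount of product, its strength, the amount of active drug and the frequency. The same statement should appear in the abstract, the Study Plan, the summary figure and the dosing-instruction sheet. The report should describe the comparator as it was actually prescribed. Which amount is right is for the investigators to establish; none is proposed here.

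The cost is a wording change and a check of the figure and the instruction sheet. A look at the issued comparator prescriptions, at most 104 / 2 = 52 at full enrolment, would support the reporting but is optional. If recruitment ran past its planned end, the corrected wording should also reach anyone still prescribing. The design, analysis and sample size stay as they are.
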